	To test the covariate effects and the effects of interactions between covariates on the primary efficacy endpoint (change in mean sitting DBP) as well as the first secondary efficacy endpoint (change in mean sitting SBP), a repeated measures general linear model (GLM) will be proposed. The GLM repeated measures procedure provides analysis of variance when the same measurement is made several times on each patient. Age, gender, body mass index, and baseline DBP will be included in the GLM model as covariates. The GLM model will be explained in detail in the Statistical Analysis Plan, approved before database lock.
	All the other continuous secondary/exploratory endpoints will be assessed across different study visits using a paired t-test or independent t-test, as applicable.
	All secondary/exploratory endpoints related to proportion of patients achieving the BP goal at Week 4 and Week 8 will be analyzed descriptively along with the relative 95% CI to assess if there is a significant difference from Week 0 where all patients were uncontrolled.
	Sample size : A total sample size of 216 patients is required to achieve 90% power at a 5% significance level assuming a difference in mean DBP from baseline (Visit 2) to 8 weeks (Visit 4) of 4 mmHg and a standard deviation for this difference of 10 mmHg. The mean change in DBP for the null hypothesis is set equal to 2 mmHg.

[figure not shown]
MENARINI	Corporate Medical Department		
	Р	Protocol Template	
Identification Number	Version Number	State	Effective date
FORM-000050125	2.0, CURRENT	Effective	08 Jan, 2021

A total number of 290 patients will be screened considering 25% of
drop-out rate, to obtain approximately 216 completed patients at the
end of the study (Visit 4).

MENARINI	Corporate Medical Department				
	Pr	otocol Template			
Identification Number	Version Number	State	Effective date		
FORM-000050125	2.0, CURRENT	Effective	08 Jan, 2021		

Study Code: MEIN/21/AmNe-Hyp/001

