6.5. Statistical Tests

The default significant level will be (5%); confidence intervals will be 95% and all tests will be two-sided, unless otherwise specified in the description of the analyses.

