16.1.3. Primary Analysis of Primary Efficacy Variable

The primary objective of this study is to test the hypothesis that

H0: There is no change in the sitting DBP prior or post combination therapy.

H1: There is a difference in the sitting DBP prior or post combination therapy.

The primary efficacy analysis will be performed for the mITT population. The above hypothesis will be tested as following:

- Change from baseline in sitting DBP from prior and post combination therapy will be tested using paired t-test. The p-value obtained from the paired t-test will be presented.
- Assumption of Normality will be investigated using Wilk-Shapiro test. If the data is found to be non-Normal, the paired t-test will be replaced by Wilcoxon signed rank test.

Document: \\weedc-vnasc01\Biosdata\Menarini\NebAml\ZZA67778\Biostatistics\Documentation\SAP\SAP_Menarini_MEIN21AmNe-Hyp001_Final_V1.0

Author: [name]

Version Number:

Final V1.0

Version Date:

11Nov2022

Template No.: CS_TP_BS016 Revision 7

Reference: CS_WI_BS005

Effective Date: 01Nov2021

- The primary endpoint will be summarized descriptively using n, mean, median, SD, Q1, Q3, minimum, and maximum.
- Only those patients for whom we have DBP assessment results available at both Week 4 and Week 8 will be considered.

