16.2.2. Analysis of Secondary Efficacy Variables

16.2.2.1. Change in mean sitting SBP between Visit 2 (Week 0) and Visit 4 (Week 8)

Change from baseline in sitting SBP from prior and post combination therapy will be compared using paired t-test. The p-value will be presented using a paired t-test comparing mean at baseline and mean at Week 8. The secondary endpoint will be presented in a descriptive manner using n, mean, median, SD, Q1, Q3, and minimum and maximum. Assumption of normality will be investigated using Wilk-Shapiro test. If violation is observed, then paired t-test will be replaced by Wilcoxon signed rank test.

Additionally, the secondary end point of change in SBP between Visit 2 and Visit 4 will be analyzed using a repeated measures GLM as described in Section 16.1.4 with Age (Years), Gender, body mass index, and baseline SBP as covariates to identify the effect of covariates and interaction between the covariates.

16.2.2.2. Change in mean sitting DBP and SBP between Visit 3 (Week 4) and Visit 4 (Week 8)

Change in sitting SBP and DBP between patients under extemporaneous combination of NEB/AML 5/5 mg versus patients uptitrated to the extemporaneous combination of NEB/AML 5/10 mg will be compared using independent samples t-test. The secondary endpoint will be presented in a descriptive manner using n, mean, median, SD, Q1, Q3, and minimum and maximum. Assumption of normality will be investigated using Wilk-Shapiro test. If the data is found to be non-Normal, the independent samples t-test will be replaced by Wilcoxon rank-sum test.

Document: \\needc-vnasc01\Biosdata\Menarini\NebAm\ZZA67778\Biostatistics\Documentation\SAP\SAP_Menarini_MEIN21AmNe-Hyp001_Final_V1.0

Author: [name]

Version Number:

Final V1.0

Version Date:

11Nov2022

Template No.: CS_TP_BS016 Revision 7

Reference: CS_WI_BS005

Effective Date: 01Nov2021

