APPENDIX 1. PROGRAMMING CONVENTIONS FOR OUTPUTS

IQVIA Output Conventions

Outputs will be presented according to the following:

[Global Bios > Processes > GBIOS Processes - Implementation Guidelines and Templates > General Guidelines and Templates > Output Conventions.](#)

Dates & Times

Depending on data available, dates and times will take the form yyyy-mm-ddThh:mm:ss.

Spelling Format

English US

Presentation of Treatment Groups

For outputs, treatment groups will be represented as follows and in the given order:

Therapy	Treatment Group	For Tables, Listings and Figures
Monotherapy	NEB 5mg	NEB 5mg
Monotherapy	AML 5mg	AML 5mg
Combination Therapy	NEB+AML (5mg)	NEB+AML (5mg)
Combination Therapy	NEB+AML (10mg)	NEB+AML (10mg)

Presentation of Visits

Visit 1 (Week -4)

Visit 2 (Week 0)

Visit 3 (Week 4)

Document: \\weedc-vnasc01\Biosdata\Menarini\NebAm\ZZA67778\Biostatistics\Documentation\SAP\SAP_Menarini_MEIN21AmNe-Hyp001_Final_V1.0

Author: [name]

Version Number:

Final V1.0

Version Date:

11Nov2022

Template No.: CS_TP_BS016 Revision 7

Reference: CS_WI_BS005

Effective Date: 01Nov2021

Visit 4 (Week 8)
Early Termination

For outputs, visits will be represented as follows and in that order:

Long Name (default)	Short Name
Screening (Visit 1)	Scr (V1)
Baseline (Week 0) or Visit 2 (Week 0)	BL(W0) or V2 (W0)
Visit 3 (Week 4)	V3 (W4)
Visit 4 (Week 8)	V4 (W8)
Early Termination	ET

Listings

All listings will be ordered by the following (unless otherwise indicated in the template):

- Treatment group (Monotherapy and Combination Therapy),
- Center-subject ID,
- Date (where applicable).

Document: \\weedc-vnasc01\Biosdata\Menarini\NebAm\ZZA67778\Biostatistics\Documentation\SAP\SAP_Menarini_MEIN21AmNe-Hyp001_Final_V1.0

Author: [name]

Version Number:

Final V1.0

Version Date:

11Nov2022

Template No.: CS_TP_BS016 Revision 7

Reference: CS_WI_BS005

Effective Date: 01Nov2021

Reference Code

- Paired t-test

```
ods trace on;  
proc ttest data=input_data h0=0;  
  paired VISITX*VISITY;  
  ods output TTests=test;  
run;  
ods trace off;
```

- Normality assumption check

```
ods trace on;  
proc univariate data=indata normal plot;  
  var change from baseline;  
  histogram /normal kernel(color=red);  
  ods output TestsForNormality=norm(where=(test="Shapiro-Wilk"));  
run;  
ods trace off;
```

- Wilcoxon Signed Rank Test

```
ods trace on;  
proc univariate data=indata mu0=0 loccount;  
  var change from baseline;  

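### A Shapiro-Wilk pre-test decides whether the primary test addresses the mean DBP change or a different location; the paired t-test should be primary regardless

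*SAP*

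**What the plan says.** The primary variable is the change in sitting DBP from Visit 2 to Visit 4. SAP 16.1.3 tests it with a paired t-test in the mITT population, checks normality by Shapiro-Wilk, and then states: "If the data is found to be non-Normal, the paired t-test will be replaced by Wilcoxon signed rank test". Protocol 12.5.2 has the same rule.

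No threshold is set for the normality test, so the general rule in SAP 6.5 is the only one available: "The default significant level will be (5%); confidence intervals will be 95% and all tests will be two-sided". The null hypothesis speaks of no change in sitting DBP and names neither mean nor median. SAP 16.1.3 asks for descriptive statistics, including the mean and SD, but for no confidence interval.

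The Protocol synopsis asks for 216 patients (90% power, 5% level) and sizes the trial on a mean, "assuming a difference in mean DBP from baseline (Visit 2) to 8 weeks (Visit 4) of 4 mmHg". The SD of the change is taken as 10 mmHg, and the null value is not zero: "The mean change in DBP for the null hypothesis is set equal to 2 mmHg". The sample code in SAP Appendix 1 instead tests zero ("proc ttest data=input_data h0=0"), and the signed-rank code also uses a null of 0.

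The rule recurs for SBP in SAP 16.2.2.1 ("If violation is observed, then paired t-test will be replaced by Wilcoxon signed rank test"), for the exploratory changes in SAP 16.3.2, and in Protocol 12.5.4 and 12.5.5. SAP 16.2.2.2 has a two-group counterpart: independent-samples t-test replaced by rank-sum.

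**The concern.** The signed-rank test is a test of the mean only if the changes are symmetric. With skewed changes it tests the pseudo-median, which lies away from the mean. The plan replaces the t-test rather than supplementing it, so the observed shape of the data decides which quantity carries the primary p-value.

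At about 216 patients the t-test has little need of normal data, while Shapiro-Wilk is sensitive enough to reject for moderate skew. The pre-test therefore tends to remove the t-test where it still works and to bring in signed-rank where its symmetry assumption fails.

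Three things are at stake: the error rate for a statement about the mean change; the match between the p-value and the mean reported beside it; and comparability between analyses. On the last, SAP 16.1.5 repeats the procedure in the PP population as a robustness check, so mITT and PP could receive different tests of different quantities.

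**Working it through.** **Inputs.** n = 216, assumed change 4 mmHg, SD 10 mmHg and sample-size null 2 mmHg (Protocol synopsis and 12.2); two-sided 5% (SAP 6.5); coded null 0 (SAP Appendix 1). Change is the later value minus baseline (SAP 6.6), so a fall is negative. Skewness is not in the documents; 0 to 1.0 is assumed.

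**Step 1: the plan's own figure.** The net difference is 4 − 2 = 2 mmHg. For a one-sample test on the mean, n = (SD × (z_alpha + z_beta) / difference)².
- One-sided 5%: (10 × (1.645 + 1.282) / 2)² ≈ 214.2, so 215; with the noncentral t, 216, and power at 216 is 90.07%.
- Two-sided 5%: (10 × (1.960 + 1.282) / 2)² ≈ 262.8, so 263; with the t, 265, and power at 216 is 83.3%.

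The 216 is thus reproduced by a one-sided t-test on a mean. That confirms the mean as the design quantity. The mismatch with the two-sided test of 0 in the SAP is a separate matter.

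**Step 2: two-stage rule under a true mean change of 0.** Changes were simulated as 10 × (G − k)/√k, with G gamma of shape k = 4/skewness². This gives mean 0, SD 10 and the chosen skewness. Each of 10,000 trials per row had 216 patients, Shapiro-Wilk at 5%, then the t-test or signed-rank test of 0, two-sided at 5%.

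| Skewness | Switch to signed-rank | Type I error, two-stage | Type I error, t-test alone | Pseudo-median minus mean (mmHg) |
|---|---|---|---|---|
| 0 (normal) | 5% | 5.4% | 5.3% | 0 |
| 0.2 | 17% | 5.6% | 5.0% | −0.17 |
| 0.3 | 34% | 6.1% | 4.9% | −0.25 |
| 0.4 | 55% | 7.0% | 4.9% | not computed |
| 0.5 | 76% | 8.8% | 4.7% | −0.42 |
| 0.75 | 98% | 14.5% | 4.8% | not computed |
| 1.0 | 100% | 22.2% | 5.0% | −0.82 |

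The Monte Carlo standard error is about 0.2 to 0.4 percentage points. Repeat runs gave two-stage error of 8.4% to 9.4% at skewness 0.5 and 22% to 24% at 1.0. For scale, the standard error of the mean is 10/√216 = 0.68 mmHg.

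**Step 3: symmetric non-normality.** With t-distributed changes on 6 degrees of freedom the switch occurs in 72% of trials, but type I error stays at 5.2%. The inflation comes from asymmetry.

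**Step 4: direction.** Each tail is nominally 2.5%. At a true mean of 0, the chance of falsely declaring a DBP reduction is about 8% at skewness +0.5 and about 1% at −0.5. At a true fall of 2 mmHg, two-stage power is 91% at skewness +0.5 and about 66% to 67% at −0.5, against about 83% for the t-test.

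**Step 5: the planned effect.** At a true fall of 4 mmHg tested against 0, both rules reject almost always. In the tabulated runs the largest gap was at skewness −1.0, 1.0000 against 0.9988, so disagreement is of the order of 0.1% of trials.

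**The case against.** The case for leaving the rule alone has real substance.

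- The decision rule is prespecified in both documents. The data choose the branch, but nobody chooses the rule after seeing the data. This stands, so it would be wrong to call the analysis unplanned.
- The null hypothesis names no parameter. Read as exchangeability of the two visits, it implies differences symmetric about 0, and signed-rank then keeps its level. The word mean in the endpoint could also refer to the average of each visit's three readings. This limits the error inflation to statements about the mean change. It does not remove the point, because the sample size is plainly for a mean change.
- The larger figures need marked skew. At 0.2 to 0.3 the switch is a minority event and the error is about 6%. A reader might infer that the trial runs at 15% to 22% type I error; the documents give no skewness and do not support that.
- A reader might also infer that the primary conclusion is unreliable. At the planned 4 mmHg change against a null of 0, the choice of test almost never alters the decision.
- The mean is reported descriptively whichever test is used. What the plan omits is a stated confidence interval for it, or an estimate that matches the signed-rank test.

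What remains is that a rule followed exactly can move the primary test off the quantity the trial was sized on, with no offsetting need at this sample size.

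**Conclusion.** The point holds as a minor improvement. Under skew, the pre-test replaces a test of the mean change with a test of the pseudo-median, and the two-stage rule loses its level for the mean. The excess is under about one percentage point at skewness 0.2, about 4 points at 0.5 and about 17 points at 1.0. It falls almost wholly in one tail: positive skew favours a false claim of reduction, while negative skew makes that claim less likely and lowers power.

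These sizes rest on 216 analysed patients, SD 10 mmHg, gamma-shaped skew, a 5% threshold for Shapiro-Wilk and a true mean change of 0. If non-normality is symmetric there is no inflation, and if the true change is near 4 mmHg the decision hardly depends on the switch. The main stake is therefore which quantity the primary p-value and report describe, rather than whether the trial succeeds.

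**What to change.** State in SAP 16.1.3 and Protocol 12.5.2 that the target is the mean change in sitting DBP. Make the paired t-test, with the mean change and its 95% confidence interval, the primary analysis whatever Shapiro-Wilk shows. Report signed-rank only as a labelled sensitivity analysis.

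Apply the same to the paired comparisons in SAP 16.2.2.1 and 16.3.2 and in Protocol 12.5.4 and 12.5.5. SAP 16.2.2.2, and the matching sentence in Protocol 12.5.4, compare two groups, so a paired test cannot serve there. Keep the independent-samples t-test unconditional, with rank-sum as sensitivity.

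Cost: no extra patients or data and no material programming, since the t-test is already coded and holds its level at this sample size. It is not only a SAP edit, however. The rule is also in the protocol, and Protocol 12.7 makes a change to the original primary analysis a substantial amendment, which under Protocol 12.6 needs ethics committee and authority approval. The SAP is dated 11 November 2022 and last patient out was planned for early December 2022, so time is short. If an amendment is not wanted, the minimum is to report the paired t-test mean change with its 95% confidence interval alongside any signed-rank result.

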16.1.4. Supplementary Analysis of Primary Efficacy Variable

A repeated measure general linear model (GLM) will be performed on the primary efficacy endpoint to test the covariate effects and the effects of interactions between the covariates for the mITT population. The GLM model will include change in mean sitting DBP as the dependent variable, repeated through visits Visit 3 (Week 4) and Visit 4 (Week 8). Age (Years), gender, body mass index (BMI), and baseline DBP are considered as the covariates.

The GLM model is

$$\text{Change from Baseline} = \text{Visit} + \text{Age} + \text{Gender} + \text{BMI} + \text{baseline DBP} + \text{Age*Gender} + \text{Age*BMI} + \text{Age*baseline DBP} + \text{Gender*BMI} + \text{Gender*baseline DBP} + \text{BMI*baseline DBP} + \text{Age*Gender*BMI} + \text{Age*Gender*baseline DBP} + \text{Age*BMI*baseline DBP} + \text{Gender*BMI*baseline DBP} + \text{Age*Gender*BMI*baseline DBP}$$

A PROC MIXED procedure, with an unstructured covariance matrix, is used for the analysis and the corresponding p-values for each of the covariates will be presented in a table.

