7.4. Multiple Comparisons/ Multiplicity

Not Applicable

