16.1.5. Sensitivity Analysis of Primary Efficacy Variable(s)

The sensitivity analyses will be conducted similar to the primary efficacy analysis including the repeated measure GLM using the PP population.

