  ODS Output TestsForLocation=test LocationCounts=LOCC_one;  
run;
```

- Exact McNemars Test

```
ods trace on;  
ods output McNemarsTest=McNemarsTest;  
proc freq data=indata order=data;  
  tables VISITX*VISITY/agree alpha=0.05 ;  
  exact mcnem;  
  weight ZZZ/zeros;  
run;
```

Document: \\neadc-vnasc01\Biosdata\Menarini\NebAm\ZZA67778\Biostatistics\Documentation\SAP\SAP_Menarini_MEIN21AmNe-Hyp001_Final_V1.0

Author: [name]

Version Number:

Final V1.0

Version Date:

11Nov2022

Template No.: CS_TP_BS016 Revision 7

Reference: CS_WI_BS005

Effective Date: 01Nov2021

- Independent sample t-test

```
ods trace on;  
proc ttest data=indata h0=0;  
class xxx;  
var change from baseline;  
run;  
ods trace off;
```

- Wicoxon Rank Sum Test

```
ods trace on;  
proc npar1way data=indata wilcoxon;  
by by_variables;  
class xxx;  
var change from baseline;  
ods output WilcoxonTest=wt;  
run;
```

- Repeated measures GLM

```
proc mixed data=indata;  
class visit sex;  
model change from baseline = Visit Age Gender BMI baseline_DBP Age*Gender  
Age*BMI_Age*baseline_DBP Gender*BMI Gender*baseline_DBP BMI*baseline_DBP  
Age*Gender*BMI_Age*Gender*baseline_DBP Age*BMI*baseline_DBP Gender*BMI*baseline_DBP  
Age*Gender*BMI*baseline_DBP;  
repeated visit;  
run;
```

Document: \\eedc-vnasc01\Biosdata\Menarini\NebAm\ZZA67778\Biostatistics\Documentation\SAP\SAP_Menarini_MEIN21AmNe-Hyp001_Final_V1.0

Author: [name]

Version Number:

Final V1.0

Version Date:

11Nov2022

Template No.: CS_TP_BS016 Revision 7

Reference: CS_WI_BS005

Effective Date: 01Nov2021

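### The supplementary GLM reads 11 covariate interactions one at a time at 5% with no joint test, giving a false interaction in about 12% to 13% of null trials per outcome and little power for real ones

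*SAP*

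**What the plan says.** SAP 16.1.4 models change from baseline in DBP at Visits 3 and 4 on visit, age, gender, BMI, baseline DBP and every product of those four covariates. The purpose is "to test the covariate effects and the effects of interactions between the covariates for the mITT population", and the output is that "the corresponding p-values for each of the covariates will be presented in a table".

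SAP 16.2.2.1 has SBP "analyzed using a repeated measures GLM as described in Section 16.1.4 with Age (Years), Gender, body mass index, and baseline SBP as covariates", the aim being "to identify the effect of covariates and interaction between the covariates". SAP 16.1.5 repeats the DBP analysis, "including the repeated measure GLM using the PP population". SAP 16.2 puts the secondary variables in both mITT and per-protocol.

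On error control, SAP 6.5 states: "The default significant level will be (5%); confidence intervals will be 95% and all tests will be two-sided". SAP 7.4 on multiplicity reads "Not Applicable". The Appendix 1 code lists the same product terms (for example "Gender*BMI Gender*baseline_DBP BMI*baseline_DBP") with no centring step and no contrast statement.

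**The concern.** The model is there to test and identify interactions, yet it never asks the single question of whether any interaction exists. It offers 11 separate p-values, each at the default 5%. A reader of the table will naturally pick out whichever falls below that level.

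Nothing in the plan tells the reader to discount such a finding. The model sits under primary and secondary efficacy. Protocol 12.7 reserves additional or exploratory status for analyses that were not prespecified, and this one is prespecified. SAP 7.5 warns about low power in subgroups, but no similar warning covers three- and four-way interactions in about 216 patients.

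Two things are at stake: a chance covariate interaction could be reported as a prespecified finding, and a real covariate effect could be missed.

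**Working it through.** **Terms.** Four covariates give 6 two-way + 4 three-way + 1 four-way = 11 interactions, plus 4 main effects = 15 covariate terms. Over two outcomes and two populations that is 15 × 2 × 2 = 60 p-values.

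**Inputs from the documents.** N = 216 and SD of change 10 mmHg (protocol 12.2), age 18 to under 65 (protocol 6.2.1), two-sided 5% (SAP 6.5), no adjustment (SAP 7.4), unstructured covariance over two visits (SAP 16.1.4).

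**The plan's own figure.** The documents give no error rate for the interaction tests; their only relevant figure is N. For 4 against 2 mmHg with SD 10, one-sided 5% and 90% power, (1.645 + 1.282)² × (10/2)² = 214.1, so 215, or 216 with the exact t. The 216 therefore reproduces as a one-sided calculation. It serves here only as N.

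**Assumptions not in the documents.** Age about 52 (SD 9), BMI about 29 to 29.5 (SD 4.5), baseline DBP about 91 to 92 (SD 6 to 7), baseline SBP about 146 (SD 10), and 50% or 70% of one gender. Narrower, wider and truncated versions were also run.

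**Benchmark.** Eleven independent tests would give 1 − 0.95¹¹ = 43.1%.

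**Simulation under no true interaction.** The two-visit unstructured model has 216 − 16 = 200 between-patient df. Each setting had 6,000 trials; near 12% the Monte Carlo standard error is √(0.12 × 0.88/6000) = 0.4 points.

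| Setting | Any of 11 p<0.05, uncentred (as written) | Any of 11, centred | Joint 11-df test, uncentred / centred |
|---|---|---|---|
| DBP, base | 12.1% | 41.8% | 5.4% / 4.9% |
| DBP, truncated | 12.4% | 41.9% | 4.8% / 5.0% |
| SBP | 12.4% | 42.5% | 5.5% / 5.1% |
| DBP, gender 70/30 | 11.3% | 39.6% | 5.2% / 5.5% |

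A simpler one-score version gave 11.4% (narrow) to 15.3% (wide) uncentred and 39% to 43% centred. A separate rerun gave 13.0% and 40.4%.

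The expected number of false positives is 11 × 0.05 = 0.55 in either parameterisation. Uncentred product terms are almost collinear, so their p-values rise and fall together and the false positives cluster in fewer trials. Centring separates them. The joint test is identical under both.

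**Power, uncentred, same kind of assumed covariates.**
- A true age-by-BMI interaction that the joint test detects in 83% of trials makes any single interaction significant in 14.5%, barely above the 13.0% seen under the null.
- A true age effect that the main-effects model detects in 85% is detected by the age term of the full model in 5%. In the uncentred full model that coefficient is the age slope at BMI and baseline BP of zero, which the data hardly inform.

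**Text against code.** SAP 16.1.4 specifies an unstructured covariance. The REPEATED statement in Appendix 1 names only the visit, with no patient identifier and no covariance type. Fitted that way, 216 × 2 = 432 rows are treated as independent. With an assumed within-patient correlation of 0.3 to 0.7, the uncentred rate rises to 19% to 31%.

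**The case against.** The strongest reply is that nothing depends on these p-values. The section is headed as supplementary, the protocol introduces the model as an addition, and the efficacy hypothesis is tested by the paired t-test or Wilcoxon test. Unadjusted covariate p-values in such an analysis are common. That stands, and it limits the importance of the point. It does not make the term-by-term tests informative.

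Four stronger readings are tempting and not supported:
- A reader might take 41% as the plan's error rate. It needs a centring step that neither the formula nor the code contains.
- A reader might call these terms treatment effect modifiers. Every assessed patient receives the combination, with no concurrent control, and the fitted model has no treatment term. They are covariate-by-covariate interactions on BP change.
- A reader might treat 60 p-values as 60 separate chances of error. The per-protocol run largely re-uses the mITT patients, and the combined rate over outcomes and populations was not computed.
- A reader might quote an all-15-term error rate. That assumes change is unrelated to baseline BP, although baseline is subtracted in forming the change.

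A further objection concerns the remedy. If the joint test is negative, four main effects are still shown unadjusted: 1 − 0.95⁴ = 18.5%, and about 18% when simulated. The whole procedure flags something in 22.5% of fully null trials, against 13.5% for all 15 terms as written. This is correct and must be stated as a cost. The lower figure as written comes with main-effect tests that have almost no power.

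Finally, the table layout is in templates that are not part of the public documents. Term-by-term display is inferred from the stated output and the model formula.

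**Conclusion.** The point holds as a weakness of a supplementary analysis. As written, at least one false interaction is expected in about 12% to 13% of null trials for each of DBP and SBP (11% to 15% over the covariate distributions tried), which is more than twice the nominal 5%. The same tests have little ability to find real interactions or real main effects.

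These figures rest on assumed covariate distributions, N = 216 and the covariance fitted as SAP 16.1.4 describes. A reader might infer that the primary conclusion is in doubt; it is not, because it does not use this model.

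**What to change.** In SAP 16.1.4, carried into 16.1.5 and 16.2.2.1 (with baseline SBP for the SBP model), specify:

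1. Test the 11 interactions once, jointly, at 5%, comparing the full model with the main-effects model by an 11-df test (a multi-row contrast, or a likelihood-ratio comparison under ML).
2. If it is not significant, report the main-effects model (visit, age, gender, BMI, baseline BP) with estimates and 95% confidence intervals, its p-values being descriptive.
3. If it is significant, show the individual interactions with Holm-adjusted p-values.
4. Label the whole analysis exploratory, and say so in SAP 7.4.
5. Reconcile the Appendix 1 code with SAP 16.1.4 by adding the patient identifier and unstructured covariance type to the REPEATED statement. The joint test does not hold its 5% level without this.

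The cost is one contrast or model comparison and a few sentences, with no new data and no change to the primary analysis. There are two downsides. The main-effect p-values stay unadjusted, with about an 18% chance of at least one false positive under a full null. Individual interactions also become harder to declare after Holm adjustment: with uncentred covariates, at least one of the 11 passes a Bonferroni threshold in only 1.2% to 1.4% of null trials. A positive joint test may therefore not identify which interaction is responsible.

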### *Study Code:* MEIN/21/AmNe-Hyp/001

### 6.2.1 Inclusion Criteria

A patient will be considered eligible for inclusion in the study only if all of the following criteria are met:

- 1. Male or female patients with Grade 1 2 hypertension with mean sitting SBP ≥140 mmHg and ≤179 mmHg and/or mean sitting DBP ≥90 mmHg and ≤109 mmHg at screening (in accordance with the 2018 ESC/ESH guidelines definition), ≥18 and <65 years of age, on monotherapy treatment either with BBs or CCBs for at least 4 weeks before Visit 1 (screening).
- 2. Patients are able to understand and have freely given written informed consent at Screening Visit.
- 3. Patients who are able to comply with all study procedures and who are available for the duration of the study.
- 4. Ability to take oral medication and willing to adhere to the drug regimen.
- 5. Female patients are eligible to participate if not pregnant, or not breastfeeding and if they refrain from donating or storing eggs. For females of reproductive potential: use of highly effective contraception (eg. method of birth control throughout the study period and for 4 weeks after study completion defined as a method which results in a failure rate of <1% per year) such as:
  - Combined hormonal contraception (estrogen- and progestogen-containing) associated with inhibition of ovulation (oral, intravaginal, and transdermal).
  - Progestogen-only hormonal contraception associated with inhibition of ovulation (oral, injectable, and implantable).
  - Intrauterine device.
  - Intrauterine hormone-releasing system.
  - Bilateral tubal occlusion.
  - Vasectomized partner (procedure conducted at least 2 months before the screening), (provided the partner is the sole sexual partner of the trial patient and that the vasectomized partner has received medical assessment of the surgical success).
- 6. A male patient must agree to use contraception during the whole study period and for at least 1 week after the last dose of study treatment and refrain from donating sperms during this period.

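### Supplementary GLM: with age, BMI and baseline DBP uncentred and all 11 interactions fitted, the covariate p-values test effects at impossible values

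*SAP*

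**What the plan says.** The protocol synopsis proposes a repeated-measures GLM for the DBP change and extends it to SBP: "as well as the first secondary efficacy endpoint (change in mean sitting SBP), a repeated measures general linear model (GLM) will be proposed". It leaves the specification to the SAP: "The GLM model will be explained in detail in the Statistical Analysis Plan, approved before database lock".

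SAP 16.1.4 gives the purpose as "to test the covariate effects and the effects of interactions between the covariates for the mITT population". The model contains visit, four covariates (age in years, gender, BMI, baseline DBP) and all of their two-, three- and four-way products. On estimation and output it says "A PROC MIXED procedure, with an unstructured covariance matrix, is used for the analysis and the corresponding p-values for each of the covariates" will be shown. SAP 16.1.5 repeats the model in the per-protocol set, and SAP 16.2.2.1 reuses it for SBP with baseline SBP in place of baseline DBP.

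The Appendix 1 reference code enters the variables as they stand ("model change from baseline = Visit Age Gender BMI baseline_DBP Age*Gender", continuing to the four-way product). Its other statements include "class visit sex" and "repeated visit". Neither document mentions centring, reference values or a hierarchical testing rule.

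**The concern.** Once a covariate appears in products with other continuous covariates, its own coefficient is its effect where those others equal zero. Eligible patients are "≥18 and <65 years of age" (Protocol 6.2.1), and a BMI or DBP of zero is impossible. The tabulated main-effect p-values would concern patients who cannot exist, with standard errors inflated by extrapolation. This GLM is the only planned test of covariate effects on the DBP change. A table of non-significant main effects could be read as evidence that baseline DBP, age, sex and BMI do not matter, when the analysis had almost no chance of showing that they do.

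A second, smaller matter is that the reference code does not implement the covariance structure stated in the text.

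**Working it through.** The plan gives no power or precision figure for this model, so there is none to reproduce.

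**1. Count of terms.** Main effects 4, two-way 6, three-way 4, four-way 1: 4 + 6 + 4 + 1 = 15 covariate terms, of which 6 + 4 + 1 = 11 are interactions.

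**2. What each test means.** Write A, B and D for age, BMI and baseline DBP, and average over gender as a class factor. The slope of change on D is

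b_D + b_AD·A + b_BD·B + b_ABD·A·B.

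The test of b_D is the slope at A = B = 0. For a patient aged 52 with BMI 29, the slope is b_D + 52·b_AD + 29·b_BD + 1508·b_ABD (52 × 29 = 1508). Any term that lacks at least one of A, B, D is conditional on a zero in the same way. Only age×BMI×baseline DBP and the four-way term contain all three, so 15 − 2 = 13 p-values depend on the origin. Numerically, centring changed those two p-values by at most 3e-12 and the other 13 by as much as about 0.97 to 1.0. This step needs no assumed data.

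**3. Inputs for the size.** From Protocol 12.2: n = 216, SD 10 mmHg. Assumed, because the documents do not give them: correlation between the Week 4 and Week 8 changes 0.5; gender 50:50; mean/SD of age, BMI and DBP of (52/8, 29/4.5, 88/7), (50/10, 28/4, 90/5) or (55/7, 30/5, 86/8); additive true effects. Visits are linked by an unstructured covariance.

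**4. Hand check, first covariate set.** Zero lies 52/8 = 6.5 SDs below mean age and 29/4.5 = 6.4 SDs below mean BMI. The median standard error of the baseline-DBP coefficient was 4.64 uncentred, 0.089 centred and 0.085 with main effects only, and 4.64/0.089 = 52. A true slope of -0.5 gives z = 0.5/4.64 = 0.11 uncentred, so power is about 5%, and z = 0.5/0.089 = 5.6 centred, so power is close to 100%.

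**5. Simulated detection rates** (1,500 trials per scenario, range over the three sets):

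| Assumed true effect | As written | Centred, same 15 terms | Main effects only |
|---|---|---|---|
| Baseline DBP, slope -0.5 | 4.5-4.7% | 97-100% | 98-100% |
| Baseline DBP, slope -0.3 | about 5% | 67-96% | 71-97% |
| Age, 0.2 mmHg per year | about 5% | 53-85% | 57-88% |
| Sex difference, 4 mmHg | 5% | 89% | 91% |
| BMI, -0.4 mmHg per kg/m² | 5% | 71-88% | 75-91% |

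For slope -0.5, taking the correlation as 0.3 or 0.7, correlating the covariates at 0.2, or restricting baseline DBP to 80-109 gave 4-6% as written and 95-100% centred. A separate simulation with other assumed covariate distributions and effects gave 4.5-5.6% as written for all four covariates, and 99% for baseline DBP (slope -0.4) centred.

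**6. Under the null.** Each uncentred term rejects in 5.0-5.6% of trials. At least one p < 0.05 among the 15 terms occurs in about 13% uncentred and about 50-53% centred. For comparison, 15 independent tests would give 1 − 0.95^15 = 54%.

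**7. Reference code.** The REPEATED statement has no SUBJECT= or TYPE=UN, no patient identifier appears in CLASS, and CLASS names sex while MODEL names Gender. If the code were completed with independent residuals, the size of a nominal 5% covariate test would be 2(1 − Φ(1.96/√(1+ρ))) = 8.6%, 11.0% and 13.3% at ρ = 0.3, 0.5 and 0.7. The visit test would have size 2(1 − Φ(1.96/√(1−ρ))) = 1.92%, 0.56% and 0.035%. These figures are conditional on that completion and do not describe what the software would do with the code as it stands.

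**The case against.** The analysis is supplementary. No success criterion or sample-size figure rests on it, and the fitted values, the visit test and the two highest-order p-values do not depend on centring. All of this stands and limits the importance of the point, but a prespecified analysis should still be able to answer its stated question.

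The code is a template that must be rewritten before it can run, and the text of SAP 16.1.4 already implies a within-patient link. That also stands: the code point is a mismatch to repair, and the error rates in step 7 are not part of the main finding.

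The count of 13 could be said to depend on how gender is coded. It survives: centring age, BMI and DBP leaves the same two p-values unchanged even when gender is entered as numeric 1/2. The interpretation does assume partial (Type 3) tests, which the SAP does not name.

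The 5% detection rate assumes additive effects. With an assumed age-by-DBP interaction of 0.04, the uncentred baseline-DBP test rejected in 8-10% of trials, which is still poor.

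The most substantive objection is that centring makes the terms nearly uncorrelated, so a chance p < 0.05 somewhere in the table becomes much more likely, and SAP 7.4 provides no multiplicity control. This is a real cost, and the fix has to deal with it.

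**Conclusion.** The concern holds. As specified, 13 of the 15 covariate and interaction p-values test effects at a zero of age, BMI or DBP that lies outside the data, and the main-effect tests have power barely above 5% even when the effects are strong. Which hypotheses are tested follows from the algebra alone. The detection rates rest on assumed covariate distributions, correlation and additive effects, but they were stable across every set tried. Per-term type I error is about 5%, and the primary paired t-test in SAP 16.1.3 is untouched. The analysis should be corrected, but the primary conclusion is not at risk.

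The code mismatch is real but secondary. The remaining discrepancies are editorial:

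- Protocol 12.5.4 gives the SBP model the same covariates as the primary analysis, which means baseline DBP, while SAP 16.2.2.1 uses baseline SBP.
- SAP 3.3 does not list that change.
- SAP 7.1 omits baseline SBP and lists Treatment, which the GLM does not contain.

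**What to change.** - In SAP 16.1.4, state that age, BMI and baseline DBP are mean-centred before products are formed, and do the same in the per-protocol repeat. In the SBP model (SAP 16.2.2.1), centre baseline SBP in place of baseline DBP.
- Label the interaction tests exploratory. Reading the covariate main effects from a main-effects model is an acceptable alternative, and it is cleaner if those effects are the main interest.
- Complete the Appendix 1 code to match the text: `repeated visit / subject=<patient ID> type=un`, with the patient identifier and one consistently named gender variable in CLASS.
- Record the SBP-model covariate change in SAP 3.3, add baseline SBP to SAP 7.1, and say there which analyses use Treatment.

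The cost is SAP wording and program edits, with no new data. The centred full model loses at most about 6 percentage points of power against a main-effects model. The price is the higher chance of an isolated p < 0.05: about 50-53% across the 15 terms and about 43% across the 11 interactions alone (1 − 0.95^11 = 43%). This is the reason for the exploratory label.
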